To investigate these hypotheses, associations of „diabetic“ micro- and macrovascular complications with different metabolic pathways, especially glycolysis, insulin resistance, impairment of insulin secretion, psychosocial factors (depression, quality of life), cognitive

parameters, as well as clinical and laboratory parameters will be examined during basic testing in ten persons with diabetes type 1, five persons with and five without hypoglycemia unawareness. Asprosin levels were then determined during fasting periods as well as after glucose and insulin administration (hyperinsulinemic clamptest). The determination of glucagon, catecholamines and cortisol takes place during the execution as well as at the end of the clamp test and are being correlated to Asprosin values.

The findings may be crucial to understanding the pathophysiology of hypoglycemia unawareness and the development of further prevention methods.

Basic testing/cross-sectional analyses:

- Do the participants already manifest diabetes late complications?
- Do Asprosin serum levels increase after 12 hours of fasting in all participants? Is the fasting- Asprosin level higher in diabetics with insulin resistance compared to diabetics without insulin resistance?
- Are the Asprosin values after glucose administration in type 1 diabetics with or without hypoglycemia comparable unawareness and were they indicative of a comparable pathogenesis?
- How do Asprosin levels alter after insulin administration in the different subgroups during a phase of lower glucose serum levels (target range 60-70 mg / dl)? Could a correlation of the asprosin concentration to the known regulating hormones eventually exist?

6. Study design and examinations, Method

It is a clinical pilot study, which will be launched mono-centric. The following examinations are included in study, which are separated into different modules as presented in the following passage.

Recruitment of study participants will take place on medical wards and in outpatient facilities of the University Hospital Heidelberg. Moreover, there will be informative events at the University Hospital Heidelberg where study participation will be offered, and our press office will be informed and will release articles in the local press to raise attention to the study. According to experience, word of mouth will be spread as well. The participants will be ten persons with diabetes type 1, five persons with and five without hypoglycemia unawareness.

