People interested in study participation can contact the Clinical Study Center via phone or e-mail. Written information will be sent by post or handed out directly. At a separate appointment, oral and written informed consent will be obtained by a study doctor, so that study participants have enough time to think.

Basic testing will take one day. On the first day are planned various non-invasive clinical routine examinations. Study participants will be invited between 10 and 12 a.m. starving. The basic tests take three to four hours, depending on the number of study participants invited on that day. Quantitative sensor testing takes approximately 90 minutes of additional time, it will be take place on the first day too. On a second day a hyperinsulinemic clamp examination is performed, which will be scheduled separately, within four weeks of basic testing.

The clamp lasts about 5 hours including the follow-up time. Initialy blood is drawn in order to measure of plasma glucose, Asprosin, insulin, C-peptide, adrenaline, norepinephrine, glucagon and cortisone concentrations, and twice for the biobank (at the beginning and end of the test) and for determining the values of the routine lab testing will be performed. In addition, a urine examination takes place. All tests will be performed according to SOPs by trained personnel.

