6.1 Study examinations

The study examinations will be organized in modules.

All substances, methods, and medical products used in the study are approved for the use in humans and will be used according to approval.

Module 1: Medical history (questionnaire) and clinical basic testing (mandatory)

Included will be known diseases, blood glucose control, present diabetic complications, medication, allergies, size, weight, and hip/waist-ratio.

Module 2: Blood and urine testing (mandatory)

- **Basic laboratory testing**

- Total blood count (Leucocytes, red blood cells, platelets, hemoglobin, hematocrit, median corpuscular hemoglobin [MCH], median corpuscular volume [MCV], median corpuscular hemoglobin concentration [MCHC])
- Clinical chemistry: Sodium, potassium, calcium, magnesium, phosphate, triglycerides, total cholesterol, LDL-cholesterol, HDL-cholesterol, Lp(a), creatinine,

suPAR, calculated GFR, GOT/AST, GPT/ALT, GGT, AP, cholinesterase, hsCRP, total bilirubin, BUN, uric acid, ferritin, transferrin, transferrin saturation, iron (Fe), total protein, albumin

- Urine analysis: urine status, albumin, protein
- **Hormones, diabetes, glucose**
 - Fasting glucose, HbA1c, TSH, Parathormon
- **Samples for biobank**
 - Plasma for metabolomics/biomarkers
Collection of different stabilized plasma samples (Li-heparin, EDTA plasma, PBMC isolation, whole blood, citrate blood, serum, urine) at a fasting state for basic characterization, as well as EDTA plasma during interventional examinations (oGTT, clamp) to analyze different biomarkers, which are linked to the development of late diabetic complications. Collected material will be stored for up to 5 years and eliminated afterwards in case it was not needed for analyses.

With the participation in the clamp study, necessary total blood volume is 270 ml.

Module 3: insulin resistance module and asprosin cinetics

- **Euglycemic hyperinsulinemic clamp study**

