It is a standard scientific test for the determination tissue sensitivity to insulin. In this study the asprosin kinetic in various hyperglycemic and euglycemic phases as well as the correlation between asprosin levels to the other known regulating hormones (adrenaline, norepinephrine, glucagon and cortisone) will be investigated. During the hyperglycemic phase, as well as at the end of the clamp test, the mechanical pain sensitivity (MPS) and the mechanical allodynia in the case of moving stimuli (DMA) are performed on both sides of the hands and feet. This in order to determine the changes in the sensibility of the skin, the sense of pain itself and sensitivity deficits with QST in the various hyperglycemic and euglycemic phases. The implementation of the QST is described in detail in page 15 of the study protocol.

The Examination-Clamp Test starts in the morning at 07:15 after a fasting period of 12 hours. Initially blood is drawn to determine plasma glucose, insulin, C-peptide, adrenaline, nor-

adrenaline, glucagon and cortisone levels. In order to construct the biobank and for the routine lab testing, blood tests are executed both at the beginning and end of the test. In addition, urine examination is also performed.

An intravenous glucose tolerance test (ivGTT) takes place, in which 1 ml / kg of glucose 30% is as bolus injected and the serum glucose is controlled over 1 hour, initially every 2 minutes and later in gradually prolonged intervals. Additionally blood tests for insulin, C-peptide and asprosin determination are executed. This test will be used to determine the pancreatic insulin reserve and to monitor asprosin kinetics during hyperglycemia.

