6.4 Course of the study

One day is scheduled for basic testing. Study participants are scheduled to arrive between 11 and 12 am in a fasting state. The basic examinations take three to four hours, dependent on the total number of patients in the outpatient clinic since some devices have to be shared with clinical routine. QST takes 90 minutes and can be performed on the same day as basic testing. On a second day a hyperinsulinemic clamp examination is performed, which will be scheduled separately, within four weeks of basic testing. The clamp lasts about 5 hours including the follow-up time. Initially blood is drawn in order to measure of plasma glucose, Asprosin, insulin, C-peptide, adrenaline, norepinephrine, glucagon and cortisone concentrations, and twice for the biobank (at the beginning and end of the test) and for determining the values of the routine lab testing will be performed. In addition, a urine examination takes place. All tests will be performed according to SOPs by trained personnel. All participants are informed of the driving prohibition for the rest of the day after enduring the Clamp test.

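### The clamp procedure omits asprosin from the fasting start draw that two other protocol sections include, and no asprosin sample precedes the 12-hour fast

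*Protocol*

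**What the plan says.** Three places in the protocol describe the blood drawn at the start of the clamp test.

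- Opening of Section 6: "Initialy blood is drawn in order to measure of plasma glucose, Asprosin, insulin, C-peptide", followed by the counter-regulatory hormones.
- Section 6.4: "Initially blood is drawn in order to measure of plasma glucose, Asprosin, insulin, C-peptide", with the same continuation.
- Section 6.1, Module 3: "Initially blood is drawn to determine plasma glucose, insulin, C-peptide, adrenaline", then noradrenaline, glucagon and cortisone. Asprosin is not in the list.

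Module 3 also fixes the state of the participant at that draw: "The Examination-Clamp Test starts in the morning at 07:15 after a fasting period of 12 hours". All three places schedule biobank blood at the start and end of the test.

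The hormone list of the first visit (Section 6.1, Module 2) reads "Fasting glucose, HbA1c, TSH, Parathormon", and asprosin appears nowhere else in that module's itemised tests. The first visit also begins fasting: "Study participants will be invited between 10 and 12 a.m. starving".

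Section 5 asks two things of the fasting value: "Do Asprosin serum levels increase after 12 hours of fasting in all participants", and "Is the fasting- Asprosin level higher in diabetics with insulin resistance compared to diabetics without insulin resistance". Hypotheses 1 and 2 in the same section concern a rise of asprosin in the low-glucose phase, without saying from which value. The SAP applies a Wilcoxon test to clamp time points that it does not name.

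**The concern.** Asprosin is the study's main variable, and Module 3 is the text that staff would follow on the clamp day. If asprosin is not requested for the first tube, the fasting value is not assayed, and the draw cannot be repeated once the glucose bolus has been given.

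Two uses depend on that value. The comparison of fasting asprosin between participants with and without insulin resistance has no other planned source. The start sample is also one of two natural references for the rise in hypotheses 1 and 2. The SAP intends the asprosin kinetics to feed power calculations for later studies, so an unclear reference would carry over into them.

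A related gap does not depend on which list is followed. To show that asprosin increases after a fast, a sample from before the fast is needed.

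**Working it through.** **Step 1. The start draw, side by side.**

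| Place | Analytes listed | Asprosin |
|---|---|---|
| Section 6, opening | 8: glucose, asprosin, insulin, C-peptide, adrenaline, noradrenaline, glucagon, cortisone | yes |
| Section 6.4 | the same 8 | yes |
| Section 6.1, Module 3 | 7: the same without asprosin | no |

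Asprosin is the only difference. The Module 3 list is split by a page break inside the word noradrenaline and runs on without a gap, so nothing has been lost in reading the file.

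**Step 2. Other asprosin samples in the schedule.**

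- First visit, Module 2: none listed.
- ivGTT, Module 3: asprosin is named, for hyperglycemia, with no times and no pre-bolus sample stated.
- 90 mg/dl hour: covered by a reference back to the hormones already mentioned; asprosin is not named in that sentence and no times are given.
- End of the 60–70 mg/dl hour: asprosin is named.

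Planned fasting asprosin values are therefore 10 of 10 under the opening of Section 6 and Section 6.4, and 0 of 10 under Module 3 read literally. The end point of the rise is clear. Of the two reasonable starting points, one is listed in two places and missing in the third, and the other is implied without a time.

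**Step 3. The 12-hour question.** The clamp day starts after the fast, and the first visit also starts fasting. No asprosin sample from before the fast is scheduled, so adding asprosin to Module 3 does not make an increase over the fast observable. It gives a fasting level, which can be compared with the level after glucose.

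**Step 4. How much the unnamed reference can matter (illustration).** The documents give no alpha, SD or correlation. Assumed here: 5 v 5, two-sided 0.05, normal changes, an exact rank comparison of the change scores, the same end sample for both scores, and both reference samples available.

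- There are C(10,5) = 252 arrangements. U ≤ 2 or U ≥ 23 covers 2 × (1 + 1 + 2) = 8 of them, so the size for one fixed reference is 8/252 = 3.2%. The next cut would give 2 × 7/252 = 5.6%, above 0.05.
- With independent errors of equal variance σ², both change scores contain the same end sample. Their covariance is σ² and each variance is 2σ², so the correlation is 0.5. If participants differ in their response or the two references track each other, it is higher. The range 0.5 to 0.9 is shown.

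| Correlation of the two change scores | Results on different sides of 0.05, true difference 1 / 1.5 / 2 SD | Error if the better of two is reported |
|---|---|---|
| 0.5 | about 25 / 36 / 33% | about 6.0% |
| 0.8 | about 17 / 25 / 23% | about 5.4% |
| 0.9 | about 13 / 18 / 17% | a little under 5% |

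These rates, obtained by simulation, describe the unnamed time points in the SAP. They do not measure the missing analyte: if the fasting sample is absent, there is only one reference left and no disagreement can arise.

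**The case against.** The strongest reply is that Module 3 is silent and does not exclude asprosin. Sections 4 and 5 say asprosin is measured when fasting, two of the three descriptions list it, and Module 3 itself states that asprosin kinetics are its purpose. An ivGTT usually has a time-zero sample, although none is stated here. Biobank blood is scheduled at the start of the test, so the value may be recoverable. The study is an exploratory pilot of ten people. All of this stands, and it makes a dropped word the likeliest explanation. It does not remove the need to correct the operative text: the planned biobank analyses in Section 8 do not name asprosin, so nothing guarantees that assay.

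A reader might infer more: that the rise would then have to be measured from a hyperglycemic ivGTT sample, so that recovery from a glucose-lowered value would pass for a response to low glucose. The documents do not support this. No section proposes an ivGTT sample as reference, the documents give no size for any fall in asprosin after the bolus, and the 90 mg/dl hour still offers a non-hyperglycemic reference even if Module 3 is followed to the letter.

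It is equally tempting to treat the 90 mg/dl sample as the plainly better reference. That hour follows the ivGTT directly, so some carry-over is possible. Either choice is defensible.

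**Conclusion.** The concern holds in a limited form. The protocol is inconsistent on whether asprosin is assayed in the fasting draw at the start of the clamp, and the version without it is the operative procedure. On a literal reading, the question on fasting asprosin by insulin resistance loses all ten planned values, and hypotheses 1 and 2 lose one of two candidate references. They do not lose both.

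The question whether asprosin increases after 12 hours of fasting cannot be answered under any version of the schedule. This conclusion needs no assumption beyond the visit times as written.

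Leaving the reference unnamed has a conditional cost only. If both samples exist, the two choices could lead to different conclusions in roughly 13% to 36% of studies over the effects and correlations shown, and picking the better one raises the error from 3.2% to between just under 5% and about 6.0%. These figures rest on the assumptions in the working and are illustrations. The correction should be made, but it does not call the design into question.

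**What to change.** 1. In Section 6.1, Module 3, add asprosin to the initial draw so that it matches the opening of Section 6 and Section 6.4. In the 90 mg/dl hour, name asprosin and give a sampling time. If clamps were already run to the Module 3 list, assay asprosin in the start-of-test biobank plasma, provided the assay accepts stored plasma.
2. In Section 5, reword the 12-hour question to what the samples can show: the fasting level against the level after glucose.
3. In the SAP, before analysis, fix one reference sample for the rise, either the fasting start or a named 90 mg/dl sample, and note possible carry-over from the ivGTT if the latter is chosen. Report the other descriptively, and do not use an ivGTT sample as reference.

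The cost is a few lines of wording and up to ten asprosin assays. If biobank plasma is used, no extra blood is drawn and the 270 ml limit is unaffected. The price of fixing the reference is one fewer p-value.

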In this pilot study, five people with and five without hypoglycemia unawareness will be recruited and comprehensively phenotyped. The participants will be type 1 diabetics with a BMI between 25 and 35 kg / m² and 18 to 75 years of age. An extensive phenotyping of the participants will be performed, which will bring important new data on type 1 diabetes and diabetes related late complications. What takes place is the characterizing of the participants regarding their Asprosin

levels when fasting and after glucose or insulin administration (hyperinsulinemic Clamp test) as well as of the diabetic late complications even in the subgroups that form. Eventually, the correlation of the asprosin serum concentration against the other regulating hormones such as glucagon, catecholamine and cortisol will be thoroughly evaluated. A platform for discussion is created in this way, one that can still not be reached through current studies.

This is to be the first study of its kind, in which plasma levels of asprosin is determined and Type 1 diabetics with and without hypoglycemia unawareness are thoroughly examined in order to identify possible differences and similarities for the better determination of the new hormone utilizing the framework of hyperinsulinemic Clamp- Tests. The intention behind is to better understand the (patho-) physiology of the hypoglycaemia unawareness, as well as to better characterize the physiological properties of asprosin.

5. Aims and hypotheses of the study

The following hypotheses shall be studied:

- Asprosin, as fast- induced protein hormone, increases serum levels in type 1 diabetics with or without diabetes late- complications during a hypoglycemic phase.
- Asprosin increases serum levels more significantly in diabetics without hypoglycemia unawareness compared to diabetics with hypoglycemia unawareness.
- There is probably no correlation between asprosin and the previous known regulating hormones.

In order to investigate these hypotheses, study participants will be initially profoundly examined in our Clinical Study Center regarding both their glycemic metabolic responses and the clinical findings relating to their possible micro- and macrovascular complications. In addition to this quality of life, well-being, depression and neuropathic pain is going to be taken into account.

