Afterwards a glucose (20%) and an insulin solution (normal insulin 1.5 mU / kg body weight) is infused via an intravenous- cannula to the right elbow in order to set serum glucose manually at a target value of 90 mg / dl for a total duration of 1 hour. During this hour blood tests for the above mentioned hormones are performed. The same test is again performed with a glucose serum level of about 60 -70 mg / dl, corresponding to physiological fasting serum glucose values after prolonged fasting periods. This is done in order to be able to assess asprosin kinetics even at lower serum glucose levels. At the end of this last hour, blood tests for the measurement of serum insulin, C-peptide, asprosin, adrenaline, noradrenaline, glucagon and cortisone concentrations is performed. Including about two hours of follow-up after intravenous administration of Actrapid, the total duration of the examination is approximately 5 hours.

Indirect calorimetry (optional)

Measurement of O₂-uptake/CO₂-emission in a resting state and starving at the beginning, and again at the end of the clamp test for determination of substrate oxidation (glucose oxidation - GOX, lipid oxidation - LOX) in a resting state and with combined insulin and glucose infusion (Cosmed Quark RMR, Cosmed Deutschland GmbH, Fridolfing).

FibroScan® measurement (optional):

This is a pain-free, non.invasive clinical routine test of liver tissue using elastography (Echosens FibroScan®, Paris, Echosens™, Frankreich) for determination of liver stiffness, which can be used for steatosis follow up.

AGE measurement (mandatory):

Non.invasive fluorescence-based measurement of advanced glycation endproducts in the skin (DiagnOptics AGE Reader[®] SU, Diagnostics Technologies B.V., Groningen, Niederlande). No risks or contraindications are known for this method.

BIA measurement (not in patients with ICD or pacemaker):

Measurement of body components using bioelectrical impedance method (MEDI CAL Biacorus[®] RX 4000, MEDI CAL HealthCare GmbH, Karlsruhe). Sticky electrodes are attached to the patient's skin, resulting in minimal electric current. This method is widely used in clinical routine. For safety reasons, it is not used in patients with ICD or pacemaker. Other than that, no risks are known for this method.

Module 4: neuropathy module (optional)

- **NSS/NDS/SAS scores**

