Asprosin dynamics relating to serum Glucose levels under controlled alteration

Statistical Analysis Plan

Heidelberg, 31/05/2017

Statistical analysis and sample size calculation

The number of 10 subjects suffices for this pilot project. The aim of the study is to assess the asprosin effect during the hyperinsulinemic clamp test as well as its correlation to the rest of known regulatory hormones. Because of the low number of participants, only non-parametric evaluations, as well as descriptive and graphical statements, are used. Depending on the parameter, relating or non-relating non-parametric tests are performed. It is a pilot study in which no large statistical calculations are possible or, currently necessary. No biometrics will be involved in the evaluation. For evaluating differences in asprosin concentrations during different time points of the clamp, Wilcoxon test will be used. For correlations between asprosin concentration and blood glucose concentration, Kendall-tau test will be used. For ruling out confounders, linear regression analysis will be performed. For descriptive analysis, median and range will be given. As software, IBM SPSS 23.0 will be used.

The effect variables determined in this study, in particular asprosin kinetics under different glucose related metabolism conditions, can be further used for possible power analysis of larger future studies.

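### Low glucose is always the last clamp phase, so the planned Wilcoxon and Kendall analyses cannot attribute an asprosin change to glucose rather than to elapsed time or insulin exposure

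*Protocol*

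**What the plan says.** Protocol section 6.1, Module 3, sets one sequence for all participants, and section 6.4 describes a single clamp day:

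- Start: "The Examination-Clamp Test starts in the morning at 07:15 after a fasting period of 12 hours", with a baseline blood draw.
- Intravenous glucose tolerance test (ivGTT): glucose is "as bolus injected and the serum glucose is controlled over 1 hour".
- First clamp phase: "Afterwards a glucose (20%) and an insulin solution (normal insulin 1.5 mU / kg body weight) is infused", in order to "set serum glucose manually at a target value of 90 mg / dl for a total duration of 1 hour".
- Second clamp phase: "The same test is again performed with a glucose serum level of about 60 -70 mg / dl", with asprosin and the other hormones drawn when that hour ends.

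No alternative order, time-control session or comparison group without the low phase is described.

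Hypothesis 1 (Protocol sections 3 and 5) is that asprosin "increases serum levels in type 1 diabetics with or without diabetes late- complications during a hypoglycemic phase". Hypothesis 2 is that the rise is larger in participants without hypoglycemia unawareness.

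The SAP states: "For evaluating differences in asprosin concentrations during different time points of the clamp, Wilcoxon test will be used". It also states: "For correlations between asprosin concentration and blood glucose concentration, Kendall-tau test will be used". It does not say whether tau is calculated on pooled samples, per participant or at one time point. It adds a linear regression to exclude confounders, naming neither model nor covariates.

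**The concern.** Hypothesis 1 is about glucose, but the schedule changes glucose, elapsed time, time since the last meal and cumulative insulin together. The Protocol summary itself says that asprosin rises in humans during fasting. An upward drift over the morning is therefore plausible on the plan's own account, and it points the same way as hypothesis 1.

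Such a drift, with no glucose effect at all, would appear as a positive Wilcoxon result and as an inverse asprosin-glucose correlation. Both documents intend the observed effects to feed power calculations for larger studies, so a misattributed effect would be carried forward.

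**Working it through.** **1. The plan's own figures.** The stated total of about 5 hours reproduces: 1 h ivGTT + 1 h at 90 mg/dl + 1 h at 60-70 mg/dl + 2 h follow-up = 5 h. The sample size of 10 cannot be reproduced, because no alpha, power, effect size or SD is given.

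**2. What each phase carries.** Assuming no gaps between phases:

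| End of phase | Time since meal | Hours of insulin infusion |
|---|---|---|
| ivGTT | 12 + 1 = 13 h | 0 |
| 90 mg/dl | 12 + 2 = 14 h | 1 |
| 60-70 mg/dl | 12 + 3 = 15 h | 2 |

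**3. Can regression separate them for 90 versus 60-70 mg/dl?** Let low = 0 at 90 mg/dl and 1 at 60-70 mg/dl, with samples at the ends of the phases. The rows (intercept, low, time in h, insulin hours) are (1, 0, 2, 1) and (1, 1, 3, 2). So time = 2 + low and insulin hours = 1 + low, exactly. The matrix has rank 2 of 4, or 11 of 13 with participant intercepts. No choice of covariates identifies the glucose term.

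**4. Kendall tau across phases.** Over the three phase ends glucose falls at each step (assuming it is still above 90 mg/dl at the end of the ivGTT). All 3 pairs of glucose with time are discordant: tau = (0 - 3)/3 = -1.0. Adding the fasting sample gives 6 pairs:

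- assumed fasting glucose 100 to 250 mg/dl: (1 - 5)/6 = -0.67
- assumed fasting glucose 80 mg/dl: (2 - 4)/6 = -0.33

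Across all samples the confounding is therefore strong but not complete, because glucose rises from baseline to the ivGTT before it falls. This applies within a person as well as to pooled samples.

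**5. Size for the Wilcoxon.** Assumptions: true glucose effect zero; normal paired change with SD 1; drift between the last two phases in SDs of that change; n = 10; two-sided 5%. Simulated rejection rates (40,000 replicates):

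| Drift (SD) | Signed-rank, n = 10 | Mann-Whitney on changes, 5 v 5 |
|---|---|---|
| 0.3 | 13% | 3% |
| 0.5 | 28% | 3% |
| 1.0 | 79% | 3% |

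With no drift the signed-rank rate is 4.7%.

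**6. The opposite direction.** A true rise of 1 SD is detected in 79% of trials with no drift, 28% with a drift of -0.5 SD and 5% with -1 SD (4,000 replicates).

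**7. What the between-group comparison can and cannot do.** Drift shared by both groups cancels, hence the 3% above. A real glucose effect shared by both groups cancels too: with an equal true effect of 1 or 2 SD in each group, the test rejects in 3%. For a true group difference of 1, 1.5 or 2 SD, power is only about 20%, 44% or 68%.

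**8. Tau within a clamped phase.** Assuming a true 1 SD rise in asprosin per 25 mg/dl fall, n = 10 and a within-phase glucose SD of 2 to 5 mg/dl, tau rejects in 5-10%. Glucose held at a target leaves little to correlate with.

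**The case against.** **The SAP makes no causal claim.** It speaks only of differences between time points, and it is a 10-person pilot with largely descriptive aims. A reader might infer that the SAP attributes those differences to glucose; its wording does not say so. This stands. But hypothesis 1 does make that link, and nothing in the SAP tells the reader that the test cannot support it.

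**Pooling is not stated.** A reader might infer that tau pools all samples as if independent. The SAP does not say how repeated samples are handled. The point does not need pooling, since a per-person tau across phases is confounded as well.

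**The SAP provides for confounders.** It does, through linear regression, but step 3 shows that this cannot work for the key contrast.

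**Fasting is not simply prolonged.** Intravenous glucose is given throughout, so time since the last meal is the accurate description. The text also gives one insulin figure and no different one for the low phase. Between the two clamp phases the confounder is therefore duration and cumulative exposure; against baseline or the ivGTT it is also insulin infusion versus none.

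**The drift sizes are assumed.** This stands. The rates in steps 5 and 6 show a range, not an expectation. The confounding itself does not depend on them.

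**Conclusion.** The point holds. For 90 versus 60-70 mg/dl, glucose, time and insulin exposure are completely confounded by design. Over all samples the confounding is strong but partial. If drift is upward, false-positive support for hypothesis 1 ranges from 13% to 79% over the assumed 0.3 to 1.0 SD; if it is downward, a true rise can be missed. These rates assume normal changes, a two-sided 5% level and end-of-phase samples.

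Two stronger readings are not supported. First, hypothesis 2 is not undermined in the same way: drift common to both groups does not bias the comparison of changes, although the groups are not randomised and similar drift must be assumed. Second, the between-group comparison should not become the basis for a glucose-specific conclusion. It answers a different question, and it rejects in only 3% of trials when both groups share a real glucose effect.

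The planned tests can stay; what needs correcting before analysis is the inference drawn from them.

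**What to change.** In the SAP:

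- **(a) Hypothesis 1.** Keep the Wilcoxon, but state that its result is *change over the clamp; glucose, time and insulin exposure not separable*, and that the regression does not remove this confounding.
- **(b) Kendall tau.** Do not interpret a tau that spans phases as a glucose effect. Where tau serves that purpose, calculate it across participants at one time point with real glucose spread, for example the fasting sample. Confirm that asprosin is measured there: Protocol sections 6 and 6.4 list it in the initial draw, but Module 3 of section 6.1 does not. Avoid tau within the clamped phases.
- **(c) Hypothesis 2.** Compare the change from 90 to 60-70 mg/dl between aware and unaware participants with an exact Mann-Whitney test. Note that shared drift cancels, that similar drift is assumed, that 5 v 5 has low power, and that this does not replace hypothesis 1.
- **(d) Descriptive check.** If at least two asprosin samples exist in the 90 mg/dl hour (the Protocol does not give the number), show their change. Note that it also reflects glucose settling after the bolus and the start of insulin, so it is not a clean measure of drift.

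The cost is SAP wording only, with no new visit, procedure or blood draw. The downside is a weaker claim for hypothesis 1.
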